*As above, we will consider the first 3 months after randomization to be the period in which participants can have a "qualifying event." For the intervention group, the qualifying event is a survey that indicates perceived problems with care coordination. For the usual care group, the qualifying event will typically be a hospital discharge or, rarely, a physician referral. Participants who have a qualifying event will then receive attention from care coordinators, with care coordination lasting for 1 month following the qualifying event (equivalent to 2-4 months after randomization, with optional continuation of care coordination at the care coordinator's discretion). Follow-up for the combined outcome of emergency department visit or hospitalization will continue for 12 months, beginning 1 month after the start of care coordination (equivalent to starting 3-5 months after randomization and ending 15-17 months after randomization).

Discontinuation:

Participants may discontinue care coordination at any time.

Measures to minimize bias:

We will use randomization to minimize bias. Masking will not be feasible for this trial, because the care coordinators will know if a patient has been discharged from the hospital or has received a survey to assess experiences with healthcare. This seems acceptable given that it is a pragmatic clinical trial, designed to determine comparative effectiveness in the real world.

Potential risks:

The risks involved in this study are minimal, as the receipt of care coordination (which seeks to facilitate communication among people involved in a patient's care) is part of standard clinical practice. The only study activity that is different from usual care is the administration of a telephone survey, which takes 7 minutes to complete. This survey has previously been successfully administered to more than 7,000 adults 65 years and older nationwide, with no adverse consequences reported by the team of people who conducted the data collection for that administration. It is theoretically possible that answering the survey could increase a respondent's anxiety about the complexities of navigating healthcare, although we expect any such increase to be mild and short-lived, because we will be providing immediate resources to

address the reported problems. The other risk is a breach of confidentiality, but we can take ample measures to minimize the likelihood that this occurs, as described below.

Steps taken to minimize risk:

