Secondary outcomes will consist of four implementation outcomes. Acceptability will be operationalized as the change in self-reported problems with care coordination at baseline vs. 1 month after the start of care coordination services. Appropriateness will be operationalized as: a) the types of problems with care coordination uncovered in response to the survey in the intervention group, and b) the frequency of different types of care coordinator activities in each group (i.e., facilitating provider-provider communication, facilitating transportation, etc.). Fidelity will be measured by tracking how many people in the intervention group are surveyed, how many report problems with care coordination, and how many of those receive care coordination services. Implementation Cost (or Efficiency) will be measured as the total number of care coordinator hours needed in each group. Acceptability will be measured with surveys, and the pre-post comparison will be made with McNemar's test to account for the paired nature of the data. The other implementation outcomes will be measured through manual review of the electronic health record, using a standardized abstraction tool, and reported with descriptive statistics.

Sample size and power:

This trial will include Medicare beneficiaries ≥ 65 years old who are: 1) attributed to NewYork Quality Care by the Centers for Medicare & Medicaid Services; 2) community-dwelling; 3) who have cardiovascular disease (CVD) or ≥ 1 CVD risk factor (defined as one or more of acute myocardial infarction, atrial fibrillation, diabetes, heart failure, hyperlipidemia, hypertension, ischemic heart disease, and stroke or transient ischemic attack), and 4) had highly fragmented ambulatory care in the past year (as a risk factor for gaps in communication among providers). We expect that approximately 6,000 individuals will meet these inclusion criteria.

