To determine how many of those 6,000 individuals we would include in the trial, we first calculated the sample size needed to determine a difference in the percentage of people in the intervention group who report a gap in care coordination at baseline vs. 1 month after receipt of care coordination services (Aim 2a). Based on our preliminary data, we assumed that 38% of people would report a gap in care coordination at baseline. Table 1 shows the sample size needed in the intervention group to find a range of effect sizes, using McNemar's test and assuming $\alpha = 0.05$, power = 80%, and correlation for paired observations of 50%. We then calculated the sample size needed to determine a significant difference in the percentage of people who experience an ED visit or hospitalization, comparing the intervention and control groups over the 12-month follow-up period (Aim 1). Using preliminary data from [name] R01 study sample, we found that 40% of Medicare beneficiaries with CVD or ≥ 1 CVD risk factor and highly fragmented ambulatory care in one year had an ED visit or hospitalization the following year. Table 2 shows the sample size needed in each group to find a range of effect sizes for that outcome, using a chi-square test, $\alpha = 0.05$, and power = 80%. Based on Tables 1 and 2, we will plan to include 400 people in the trial (200 per group), which will enable us to find statistically significant and clinically meaningful differences for both Aims.

Table 1. Sample size needed in the intervention group for change in self-reported gaps in care coordination pre- vs. post intervention

Effect size	Sample size
38% \pm 10%	178
38% \pm 12.5%	113
38% \pm 15%	79

Table 2. Sample size needed to detect difference in primary outcome between groups

Effect size	Sample size
40% \pm 15%	346 (173 per group)
40% \pm 20%	194 (97 per group)
40% \pm 25%	124 (62 per group)

The analysis will use all randomized participants with an intention-to-treat approach. The base case analysis will use complete data, and a sensitivity analysis will use multiple imputation for missing covariates.

H. DIRECT ACCESS TO SOURCE DATA

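### The acceptability re-survey is dated only from the start of services, so the McNemar test as written pairs almost only baseline positives, which is not the sample that Table 1 assumes

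*Combined protocol and SAP*

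**What the plan says.** Section G, Analysis plan, defines acceptability as "the change in self-reported problems with care coordination at baseline vs. 1 month after the start of care coordination services" and assigns McNemar's test to it. Section G, Sample size and power, describes the same quantity as "percentage of people in the intervention group who report a gap in care coordination at baseline vs. 1 month after receipt of care coordination services". It states that "we assumed that 38% of people would report a gap in care coordination at baseline" and uses alpha 0.05, 80% power and a "correlation for paired observations of 50" per cent. Table 1 then asks for 178, 113 or 79 people in the intervention group for changes of 10, 12.5 or 15 points.

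Section C, Expected duration, sets the route into services: "For the intervention group, the qualifying event is a survey that indicates perceived problems with care coordination". Under Intervention arm in the same section, people who screen negative get the coordinator's contact details and may call. No re-survey is mentioned for them. The lists of aims and endpoints in sections B and C say only that acceptability compares after with before, without dates. Figure 2, the participant timeline, is not reproduced in the readable text.

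**The concern.** The timing rule and the sample size calculation describe different sets of people. Table 1 treats the pairs as a sample of the whole intervention group, of whom 62% are negative at baseline. A survey dated from the start of services reaches those who start services, and these are almost entirely baseline positives. Some negatives may start later, for instance by calling the coordinator. The others have no date, and neither do positives who decline.

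A person selected for being positive can only stay positive or improve. McNemar's test compares the two directions of change, and here one direction is closed by selection. Ordinary response variation then appears as improvement (regression to the mean). Aim 2 is meant to inform dissemination, and this is its only planned significance test, so a spurious result could be read as evidence that patients found the approach acceptable.

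**Working it through.** **1. Reproduce Table 1.** Inputs from Sample size and power: p1 = 0.38, correlation ρ = 0.5, alpha 0.05 (taken as two-sided, which is what matches), power 80%, p2 = p1 − d.

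- p11 = p1·p2 + ρ·√(p1·q1·p2·q2), with q = 1 − p
- positive-to-negative b = p1 − p11; negative-to-positive c = p2 − p11; pd = b + c
- n = [1.96·√pd + 0.8416·√(pd − d²)]² / d²

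| d | b | c | n | Table 1 |
|---|---|---|---|---|
| 0.10 | 0.1646 | 0.0646 | 177.6 | 178 |
| 0.125 | 0.1773 | 0.0523 | 113.0 | 113 |
| 0.15 | 0.1905 | 0.0405 | 78.2 | 79 |

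All three rows match after rounding up. The c column (6.5%, 5.2%, 4.0% of pairs) can come only from people negative at baseline, so Table 1 needs them to be re-surveyed.

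**2. What the literal timing delivers.** 200 × 0.38 = 76 positives if all 200 complete the screening survey. If 70-80% of them take up services (the usual-care engagement rate in section C, assumed to apply here), there are 76 × 0.70 = 53 to 76 × 0.80 = 61 pairs.

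**3. Positives only, no true change.** With p1 = p2 = 0.38, the chance that a positive turns negative is 1 − p11/0.38 = 0.62 × (1 − ρ). At ρ = 0.5 this is 0.31, or about 24 of 76. The opposite cell is zero. The exact two-sided p-value with b one-way changes is 2 × 0.5^b: 0.0625 at b = 5 and 0.031 at b = 6. The exact test therefore rejects when b is 6 or more. The plan names no variant; the uncorrected asymptotic statistic equals b here and exceeds 3.84 from b = 4. Binomial probability of rejecting with the exact test (correlations other than 0.5 are assumed):

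| ρ | 53 pairs | 61 pairs | 76 pairs |
|---|---|---|---|
| 0.5 | 0.9998 | >0.9999 | >0.9999 |
| 0.7 | 0.946 | 0.980 | 0.997 |
| 0.8 | 0.656 | 0.784 | 0.922 |
| 0.9 | 0.109 | 0.176 | 0.332 |
| 0.95 | 0.006 | 0.011 | 0.031 |

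At ρ = 0.9 the asymptotic version rejects 42-70% of the time.

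**4. Some negatives start services.** Assume that 5%, 10% or 20% of the 124 negatives (6, 12 or 25 people) do so and are paired with 76 positives; each turns positive with probability 0.38 × (1 − ρ). False improvement is then declared 99.99%, 99.9% and 96.7% of the time at ρ = 0.5; 97.7%, 93.3% and 77.4% at 0.7; and 28%, 24% and 17% at 0.9.

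**5. Whole surveyed arm, no true change.** For 140 to 200 pairs and ρ from 0.5 to 0.9, the exact test rejects 1.5-3.6% of the time, within the nominal 5%.

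**The case against.** The strongest reply is that the plan already means the whole arm. The sample size text speaks of the intervention group at 38% positive, and on that reading the test is sound and only a clause is missing. This is probably the intent, but the only date written down does not deliver it. Figure 2 may supply the date; if so, only the text needs aligning.

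A second reply is that the correlation may be well above 0.5. The survey asks about the past 6 months. If the re-survey keeps that recall, two surveys about one month apart share roughly five months. This stands, and the figures depend on it: near 0.95 the excess disappears under the exact test. Still, 0.5 is the plan's own value.

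Third, pairs may be fewer. If 70-80% applies both to survey participation and to service uptake, there are 200 × 0.7 × 0.38 × 0.7 = 37 to 200 × 0.8 × 0.38 × 0.8 = 49. Rejection then stays above 98% at ρ = 0.5 but falls to 31-58% at 0.8.

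Fourth, assessing acceptability among service recipients is a legitimate choice. That is so if it is reported descriptively; it does not rescue a test of no change.

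A reader might also infer that the statement "The analysis will use all randomized participants with an intention-to-treat approach" obliges the McNemar test to include everyone. It does not carry that weight. It would bring in the usual-care arm, for which no baseline survey is described. The Analysis plan gives the principle alongside the between-arm regressions, and the next sentence sets a complete-data base case. The argument rests on Table 1 alone.

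**Conclusion.** The point holds and should be fixed. The readable text gives no re-survey date to intervention-arm participants who do not start services, while Table 1 requires them. Followed literally, the test would nearly always report improvement at the plan's own correlation even if nothing changed. At 0.9 the false-positive rate would still be about two to seven times nominal (exact test, 53 to 76 pairs). These rates assume 38% positive at baseline, no true change and, below 76 pairs, the usual-care uptake rate.

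Two stronger readings are not supported. One is that the trial is too small for Aim 2a: 200 exceeds every row of Table 1, so no power objection follows. The other is that the main result is compromised: this is a secondary implementation outcome without a control group, and the defect does not touch the primary endpoint. Confidence is medium because Figure 2 cannot be read.

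**What to change.** In both parts of section G, state that McNemar's test uses every intervention-arm participant with a baseline survey and a re-survey, whether positive or negative at baseline. Keep the existing re-survey date for those who start services. For those who do not (screen-negatives, and positives who decline), set it one month after the screening survey. Report change among baseline positives or service recipients only as a percentage with a confidence interval, without a test against zero, and note the expected regression to the mean. If negatives will not be re-surveyed, drop the McNemar test and say that Table 1 does not apply.

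Also state the re-survey's recall period, describe the result as an uncontrolled pre-post change, and label Table 1's figures as completed pairs (178 is 89% of 200). If Figure 2 already gives the date, repeat it in the text.

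Re-surveying negatives raises one matter to settle beforehand. With 200 pairs at ρ = 0.5, about 200 × 0.1178 = 24 people would be newly positive with no true change, or 200 × 0.0646 = 13 with a 10-point fall. Section C, Expected duration, makes "the first 3 months after randomization to be the period in which participants can have a" qualifying event, and says that outcome follow-up "will continue for 12 months, beginning 1 month after the start of care coordination". The handling of a new positive answer must be reconciled with that text, so that an outcome survey does not alter the intervention or the follow-up window unnoticed.

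The cost is wording plus 124 × 0.70 = 87 to 124 seven-minute calls to screen-negatives (participation assumed), or about 10 to 14.5 hours before call attempts. If 20-30% of 76 positives decline services, add 15 to 23 calls. Log this time separately from the coordinator-hours outcome.

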Intervention arm: The individuals who are randomized to the intervention arm will each receive an initial call from a care coordinator in the 3 months following randomization, which we will refer to as the "screening" call. The care coordinator will explain care coordination services as they usually would and offer to administer a survey to see if the patient is eligible for care coordination. If the patient agrees, the care coordinator will administer a previously validated telephone survey on perceptions of care coordination (see Kern et al. J Gen Intern Med 2020;35:3517-24). The care coordinator will document the survey responses in customized data entry forms that we will develop in REDCap, a secure web-based data management platform. If the patient responds to the survey in a way that indicates a perceived problem with care coordination in the past 6 months (i.e., a "positive" response to greater than or equal to 1 of 8 questions, as defined previously), then we will consider this a "positive screening." The REDCap tool will notify care coordinators at the end of the survey if the survey indicates a "positive screening." For patients and proxies whose screening calls were "negative" (not revealing a perceived problem with care coordination), the care coordinators will give them their contact information and invite them to reach out with any questions or concerns. For patients and proxies whose screening calls were "positive," care coordination will start narrowly, with the care coordinator seeking to understand the survey responses (exactly what the patient or proxy thinks is not working well and why). The care coordinator will then seek to address the issue, documenting the process in the EHR. The care coordinators will be free to engage in broader care coordination activities (e.g., general medication reconciliation, reviewing upcoming appointments, arranging transportation, etc.) at their discretion. The length and frequency of interactions between the care coordinator and patient or proxy will vary with the patient's needs and care coordinator's discretion. Patients will be followed for a minimum of 30 days and a maximum of 1 year.

Expected duration:

Participation will last up to 16 months after randomization. The events of the study are depicted below (Figure 2) and described in text that follows.

Figure 2. Timeline of events for each participant (not to scale)

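### Does the plus-minus label in Tables 1 and 2, which hides opposite directions of effect, undermine the planned sample size of 400?

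*Combined protocol and SAP*

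**What the plan says.** Section G, Sample size and power, gives two calculations. For the pre-post comparison in the intervention arm, "Table 1 shows the sample size needed in the intervention group to find a range of effect sizes". The inputs are McNemar's test, a baseline of 38% reporting a gap, alpha 0.05, power 80% and a paired correlation of 50%. Table 1 carries the title "Sample size needed in the intervention group for change in self-reported gaps in care coordination pre- vs. post intervention" and lists 178, 113 and 79 for plus or minus 10, 12.5 and 15 points.

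For the primary outcome, "Table 2 shows the sample size needed in each group to find a range of effect sizes for that outcome, using a chi-square test". The baseline is 40%, alpha 0.05 and power 80%. Table 2 lists 173, 97 and 62 per group for plus or minus 15, 20 and 25 points.

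The plan then concludes: "Based on Tables 1 and 2, we will plan to include 400 people in the trial (200 per group"). It does not say which direction of change each n was computed for, or whether alpha is one- or two-sided.

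**The concern.** A plus-minus effect with a single n reads as a claim that the n gives 80% power in either direction. Sample size for proportions is not symmetric about 38% or 40%, because the variance moves with the second proportion. One n can be exact for one sign only, and the label is true for both signs only if the larger n is printed. Table 2 prints the larger and Table 1 the smaller, so the same symbol means different things in adjacent tables. The plan rests its total on these tables. If a mislabelled row had set the sample size, the trial could have been short of power in a direction that the table appears to cover.

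**Working it through.** **Inputs** (all from section G, Sample size and power): the baselines, effects, power and correlation given above. Two-sided alpha 0.05 is tried first, with z = 1.960 and 0.8416.

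**Table 1, formula.** Let p1 = 0.38, p2 be the follow-up proportion and d = |p2 − p1|.
- Both-positive cell: p11 = p1·p2 + 0.5·√[p1(1 − p1)·p2(1 − p2)]
- Discordant share: ψ = p1 + p2 − 2·p11
- n = (1.960·√ψ + 0.8416·√(ψ − d²))² / d²

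*Reproducing the first row as a decrease, 38% to 28%.* p11 = 0.1064 + 0.5·√(0.2356 × 0.2016) = 0.2154, so ψ = 0.2293. Then n = (1.960 × 0.4788 + 0.8416 × 0.4683)² / 0.01 = 177.6, which rounds up to the printed 178.

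*The same row as an increase, 38% to 48%.* p11 = 0.1824 + 0.5·√(0.2356 × 0.2496) = 0.3036, so ψ = 0.2527. Then n = (1.960 × 0.5027 + 0.8416 × 0.4926)² / 0.01 = 196.0.

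| Change from 38% | Printed n | n, decrease | n, increase | Power at printed n, decrease / increase | Power at 200 pairs, decrease / increase |
|---|---|---|---|---|---|
| 10 points | 178 | 177.6 | 196.0 (196) | 80.1% / 76.1% | 84.5% / 80.8% |
| 12.5 points | 113 | 113.0 | 127.5 (128) | 80.0% / 75.0% | 96.3% / 94.1% |
| 15 points | 79 | 78.2 | 90.03 (91) | 80.4% / 74.5% | 99.5% / 98.8% |

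Enumerating the asymptotic McNemar test at the printed n gives 77.1%, 77.5% and 77.8% for the increases. The shortfall there is therefore 2 to 3 points, somewhat less than the formula suggests.

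**Table 2, formula.** With p̄ = (p1 + p2)/2, n per group = (1.960·√[2p̄(1 − p̄)] + 0.8416·√[p1(1 − p1) + p2(1 − p2)])² / (p1 − p2)².

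*First row as an increase, 40% to 55%.* p̄ = 0.475, and n = (1.960·√0.49875 + 0.8416·√0.4875)² / 0.0225 = 172.8, printed as 173.

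*First row as a reduction, 40% to 25%.* p̄ = 0.325, and n = (1.960·√0.43875 + 0.8416·√0.4275)² / 0.0225 = 151.9.

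| Change from 40% | Printed n per group | n, increase | n, reduction | Power at printed n, reduction | Power at 200 per group, reduction / increase |
|---|---|---|---|---|---|
| 15 points | 173 | 172.8 | 151.9 (152) | 84.9% | 89.6% / 85.4% |
| 20 points | 97 | 96.9 | 81.2 (82) | 86.6% | 99.3% / 98.1% |
| 25 points | 62 | 61.4 | 48.9 (49) | 88.6% | above 99.9% / 99.9% |

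**Sidedness.** One-sided alpha 0.05 gives 140, 89 and 62 (decrease) or 155, 101 and 71 (increase) for Table 1, and 120, 64 and 39 (reduction) or 136, 77 and 49 (increase) for Table 2. None of these sets matches what is printed. Both tables are two-sided.

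**Effect on the planned size.** The largest requirement over both tables and both directions is 196 (Table 1, 10-point increase). The plan has 200 per group, so 200 − 196 = 4 remain in that worst case. For the 10-point decrease, 200 − 178 = 22 remain.

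**The case for a change.** The best case for acting is that the label is wrong as printed. All six values match the stated tests exactly in one direction each, so the asymmetry is not an accident of method. Table 1's printed n do not give 80% power for a rise. The text speaks of a difference without a sign, the calculation is two-sided, and the total is explicitly based on these tables. The correction would cost one line. The label also suggests 22 spare pairs in either direction for a 10-point change, when there are only 4 for a rise.

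The arithmetic in that case stands in full, but the consequence does not. Section C (Intervention arm) says of a positive screen that "The care coordinator will then seek to address the issue", so a fall in reported problems is the evident target, and for a fall Table 1 is exact. The 74.5% to 76.1% power belongs to samples of 178, 113 and 79, which nobody plans to enrol. Table 2 is valid for both signs and conservative for the hoped-for reduction. Writing that alpha is two-sided would be good practice, but it only records what the figures already imply.

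One caution remains. The power at 200 pairs assumes that every intervention participant supplies both surveys and that the asymptotic McNemar test is used. With the exact version, power at 200 for a 10-point change is about 82% for a decrease and 78% for an increase; the plan does not say which version is meant. Survey completion is a separate question, and relabelling the table would not answer it.

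**Conclusion.** The concern is right about the label and does not call for a change to the plan. Table 1's figures are correct two-sided requirements for decreases from 38%, and the plus half of its label understates the need by 18, 15 and 12 pairs (196 − 178, 128 − 113, 91 − 79). Table 2's figures are correct for increases from 40% and exceed the need for reductions by 21, 15 and 13 per group (173 − 152, 97 − 82, 62 − 49). No row in either direction needs more than 196 against the planned 200, so the sample size, design, analysis and interpretation of results are untouched. It is a clerical slip that a reader can resolve from the inputs given. If the document is revised for other reasons, Table 1 could be headed as decreases.

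This rests on the plan's own inputs (38%, 40%, correlation 0.5, power 80%), the normal-approximation formulas that reproduce its tables, and complete pairs from all 200 intervention participants. It does not show that 400 is adequate in other respects.
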